The goal of the overall grant is to develop warnings to promote greater understanding of harms and to reduce WTS behavior among young adults. We have used a systematic, evidence-driven, rigorous approach to develop waterpipe warnings and test these newly developed warnings in two contexts: (1) on waterpipe tobacco packaging; and (2) in an ecologically valid waterpipe café setting. In Aim 1, we developed text and pictorial waterpipe tobacco warnings to effectively communicate a broad range of health harms. We first developed 30 text warnings based on three themes: acute health harms, chronic health harms, and correcting misperceptions. We tested these warnings in a national survey to determine the five most effective text warnings (IRB00062703). We then selected three illustrative images of the health effects presented by the warnings for each of these warnings, plus the federally mandated nicotine warning. We conducted an experiment to determine the most effective image for each of the six warning messages (IRB00080199). In Aim 2 (IRB00091946), we compared the effects of pictorial warnings versus the text-only warnings and a no-warning control placed on fictional packaging on WTS intentions.

Warning placement on packaging and at the point-of-sale is typically the result of legal mandates. In order to approximate the impact of a legal mandate to require health warnings at the point-of-sale, we will partner with places that sell waterpipe tobacco for use onsite. These places may be cafés, restaurants, lounges, bar, etc. (herein referred to as “hookah cafés”). Conducting an experiment where hookah café customers are exposed to waterpipe warnings will allow us to test the impact of the warnings on actual behavior, in the absence of legal mandates. In this experiment (Aim 3), we will conduct a cluster randomized crossover trial with up to 32 hookah cafés in Atlanta, GA (1 pilot and 31 trial cafés). We plan to overenroll cafés to account for dropout/early termination. The goal is at least 20 cafés with 15 participants per arm. Each café will serve as its own comparison as it cycles through the two trial arms: intervention (text warning) and control (no warning). The pictorial warning condition was removed in July 2024 after consultation with E&W and NCI regarding unwillingness of cafés to allow placement of pictorial warning signs. We will randomly select one of four health warning messages from Aim 2 to be displayed in each of

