Ewald & Wasserman (E&W) will conduct the Aim 3 cluster randomized crossover trial at up to 32 hookah cafés (1 pilot and 31 trial cafés) in Atlanta, GA. This trial will be conducted entirely in the field at the participating cafés. Hookah cafés will be recruited to partner with the research team, which involves allowing participants to be recruited and data collection to occur outside the café prior to café entry and after café exit on at least two data collection periods (across the two trial arms). Cafés must also agree to allow the research team to post health warnings about hookah smoking in the cafés on some of the days of data collection. E&W will be responsible for the recruitment of hookah cafés, hiring of field staff, training of field staff on data collection procedures (in conjunction with the Wake Forest study team), and implementing all data collection procedures. Data collection will involve field research at the hookah cafés. Field staff will approach potential participants before they enter the café to assess interest in the study and eligibility. For those eligible, field staff will complete the consenting process, administer a brief survey on tablet computers, collect expired carbon monoxide breath measurements, and distribute incentives at two time points: before participants enter the café and after they exit. Additionally, field staff will debrief participants at the end of the study. E&W will also be responsible for all participant payments. Finally, E&W will be responsible for printing, implementing, and removing the warning signs at waterpipe cafés.

Methods and Measures

Design

The design of the study is a cluster randomized crossover trial, where the hookah café is the cluster and randomization is at the cluster level. Each hookah café will serve as its own control and will be used for data collection for both study arms: (1) intervention, and (2) control. Each café will start in the no warning control arm to avoid the potential for contamination, since customers may visit the same café on multiple days. In the intervention arm, cafés will display one of four text warnings. In the intervention arm, warning messages will be displayed at various agreed-upon locations in the café, such as on hookah pipes, tables, countertops, walls, and menus. The goal is to maximize the potential for customers to be exposed to warnings.

Setting

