- Does not have capacity to participate as determined by the staff member conducting eligibility screening

Sample Size

- We will enroll up to 1,560 participants in total, across the 32 cafés (this includes up to 30 participants per night, per café. The goal is 15 **completions** per night, per café).

Interventions and Interactions

Intervention Arm

Study staff will place signs containing a text-only warning (selected from a pool of four warnings on lung damage, heart damage, carbon monoxide poisoning, and stunting fetal growth tested in WT Warnings Aim 2 – IRB00091946) in various locations around the café, as agreed upon with the café owner or designated representative. Locations may include the hookah pipes, tables, interior wall signs, countertop signs, menus,

and bathroom signs (see Figure 1. Table Sign). Sign placement and quantity may differ between cafés. Signs will be removed by study staff at the end of each data collection period.

Control – No Warnings

In the Control arm, there will be no signs placed by the study team at any location within the café.

Data Collection

The timing of data collection periods will be agreed upon in advance between the study team and the café owner, manager, or their designee. When the data collectors first arrive at the café, they will introduce themselves to the café point person and place signs in the agreed-upon locations and will document the locations in the café record (on intervention nights). Additionally, photographs of sign placement will be taken.

The study team will set up tables outside the café, where data collection will be completed. In 2017, we completed a pilot study to test these methods (IRB00044196), which worked well. Data collection will be conducted during café hours, when young adults are most likely to visit waterpipe cafés, based on the advice from café employees. Data collectors will approach individuals before they enter the café to determine interest in the study. Interested individuals may also approach the data collectors. Data collectors will conduct eligibility screening with interested individuals (described above).

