The sample size will allow us to detect meaningful differences in the eCO boost between study arms. We estimate the minimum difference in eCO boost detectable between the two arms (intervention vs control) with 80% power between two periods I using a cluster randomized crossover trial design with a minimum of 20 cafés, each with completed data for 30 café patrons (15 per arm). Sample size is based on formulae from Giraudeau et al. (2018) that takes into account both the intraclass correlation coefficient r (correlation within a café) and the inter-period correlation h induced by the crossover design.¹³ We consider both small and moderate ICCs or $r=0.10$ and $r=0.30$ and a smaller h specified to be half of r as recommended by Donner et al. (2004).¹⁴ A review of the literature¹⁵⁻¹⁸ suggests a standard deviation of $s=30$ parts per million (ppm) for the change in eCO. Based on these assumptions, we will have 80% power to detect differences in eCO boost between two periods of 8.81ppm for a low r and 11.78ppm for a moderate r . In one of the few studies in waterpipe cafés, the mean absolute change in CO was 51.7ppm with a relative boost of 795%.¹⁵ we are more than sufficiently powered to detect differences this large as well as much smaller changes in the range of 8.81ppm to 11.78ppm. We can convert this to number of fewer puffs based on data that a single puff results in a 0.4ppm eCO boost.¹⁹ We will be able to detect a reduction of between 22.0 and 29.4 puffs.²⁰ This is consistent with the reduction in mean puffs (26.0) found in the lab-based pilot study of WTS warnings.²¹

A hierarchical linear modeling (HLM) approach (model C1 in Turner et al. 2007) will be used for the analysis.¹³⁸ In contrast to cluster-level methods, which aggregate data, hierarchical modeling offers more flexibility and allows us to incorporate both café-level and individual-level covariates, as well as the correlation

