of individuals within study arm within cafés. We let eCO_{ijk} represent the outcome measurement for individual k within study arm j within cluster (café) I , assumed continuous and normally distributed. The model will include a fixed effect for study arm (intervention or control) and random cluster and cluster-arm effects. Models will adjust for individual-level sociodemographics and tobacco use at baseline. In secondary analyses, we will examine the impact of sociability of waterpipe behavior by adjusting models for the number of people with whom the individual is smoking in the café. Secondary analyses will examine the impact of text versus pictorial warnings. These hierarchical models will be fit using PROC MIXED in SAS. Because the intervention effect is estimated within clusters, it is also adequate to model fixed cluster effects but retain random cluster-arm effects. Turner (2007) demonstrated through simulation that these two models perform similarly with 18 clusters with slight differences depending on the degree of correlation. We will examine both approaches as a sensitivity analysis.²² Using the same HLM modeling approach, we will perform analyses on secondary outcomes shown in Table 5.

Human Subjects Protection

Overview

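### The arm comparison is called randomised, but every café runs control first, so an order effect cannot be separated from the warning effect, and the plan does not say so

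*Combined protocol and SAP*

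**What the plan says.** The introductory section states that "we will conduct a cluster randomized crossover trial with up to 32 hookah cafés", and the Design section adds that "randomization is at the cluster level". The Analytical Plan bases the sample size on the same label, "using a cluster randomized crossover trial design with a minimum of 20 cafés".

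The Design paragraph that carries the label also fixes the order: "Each café will start in the no warning control arm to avoid the potential for contamination". The reason given is that customers may visit the same café on several days.

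The only random selection described is of the message: "We will randomly select one of four health warning messages from Aim 2 to be displayed in each of" the partner cafés. Nothing says that arm, or order of arms, is randomised.

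On the number of visits, the Roles section asks cafés to allow data collection "on at least two data collection periods (across the two trial arms". Subject Selection Criteria and the Analytical Plan set 15 completers per café per arm, and Sample Size says "The goal is 15 completions per night, per café".

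For the primary analysis, "The model will include a fixed effect for study arm (intervention or control) and random cluster and cluster-arm effects". Models also adjust for individual sociodemographics and baseline tobacco use. There is no term for period, order or calendar time. The sensitivity analysis replaces random café effects with fixed ones.

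**The concern.** Randomising the order of arms is what protects a cluster crossover against changes between the first and second period. Here the order is the same in every café. Randomising the message supports comparisons between messages. It does not support the comparison of warning with no warning, which is the stated objective and the contrast that was powered.

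Using each café as its own control removes stable differences between cafés. It does not remove a change from first to second visit that is shared across cafés. A shared fall in eCO boost would look like a warning effect, and a shared rise would hide one. The confidence interval would reflect neither.

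The plan contains one possible source of such a change. People already approached on an earlier night are ineligible later, so frequent patrons may be under-represented on the warning night. The size and direction of this are unknown. Analysing within-person eCO change and adjusting for baseline tobacco use may absorb part of it.

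As written, the primary result would carry a randomised label that the arm comparison does not earn, with no stated limitation.

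**Working it through.** **Nights per arm.** The number is inferred, not stated. With 15 completers per arm and 15 completions per night, the planning basis is one night per arm. The enrolment cap agrees: 26 cafés × 2 nights × 30 = 1,560.

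**Can arm and order be separated?** Take café-night means for 20 cafés, with 20 café effects plus arm plus a period term:

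| Design | Rows | Rank / columns | Consequence |
|---|---|---|---|
| Control then warning, all cafés | 40 | 21 / 22 | Arm and period are the same column; a common shift passes through with factor 1.00 |
| Control, control, warning; free effect per night | 60 | 22 / 23 | Arm still not estimable |
| Control, control, warning; linear night trend | 60 | 22 / 22 | Estimable only under assumed linearity; arm SE 2.0 times that without the trend (equal, independent café-night errors) |
| Order split 10/10 | 40 | 22 / 22 | Both estimable; arm SE ratio 1.00 |

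Extra nights therefore do not cure the problem while control always comes first. Staggered start dates could inform a shared calendar trend, but not a first-visit/second-visit effect. The planned fixed-café sensitivity analysis uses the same within-café contrast and inherits the same bias.

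**The plan's own figure.** Inputs from the Analytical Plan: SD 30 ppm, k = 20 cafés, m = 15 per arm, r = 0.10 or 0.30, h = r/2. Alpha is not stated; two-sided 0.05 is assumed and reproduces the plan.

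SE = 30 × √(2 × [1 + 14r − 15h] / 300)

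- r = 0.10: bracket = 1 + 1.4 − 0.75 = 1.65; SE = 3.146 ppm; × 2.80 = 8.81 ppm (plan: 8.81).
- r = 0.30: bracket = 1 + 4.2 − 2.25 = 2.95; SE = 4.207 ppm; × 2.80 = 11.79 ppm (plan: 11.78).

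**Effect of a common shift (illustration only).** The shift sizes are assumed. The largest, 5.17 ppm, is 10% of the 51.7 ppm mean change that the plan cites. Rates use a noncentral t with 19 df and noncentrality shift/SE for the false-reduction rate, or (true reduction − shift)/SE for power.

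| Shift (ppm) | False-reduction rate, downward shift, no true effect: r = 0.10 / 0.30 | Power, upward shift, true reduction 8.81 / 11.78 ppm: r = 0.10 / 0.30 |
|---|---|---|
| 0 | 2.5% / 2.5% | 76% / 76% |
| 1 | 4.9% / 4.1% | 65% / 68% |
| 2.25 (r = 0.10) or 3.0 (r = 0.30) | 10% / 10% | 51% / 51% |
| 5.17 | 34% / 21% | 19% / 32% |

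Power starts at 76% rather than the plan's 80% only because t with 19 df replaces the normal approximation. On the plan's normal basis, the 2.25 or 3.0 ppm shift takes power from 80% to 55%.

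**The case against.** The strongest reply is that this is a matter of description. Control-first is printed openly beside the label and has a sensible reason, since a patron who saw signs on an earlier night could carry that exposure into a later control night. That stands, and it is why the order itself need not change. It does not make the randomised label correct, and it does not supply the missing limitation.

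The one-night-per-arm reading is indeed an inference, because the Roles section allows more visits. The exact two-night aliasing depends on it; the confounding does not.

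Bias requires a shift in a common direction across cafés, and the documents show none. Random night-to-night variation is already carried by the café-by-arm effect and by h being smaller than r. Scheduling at each café's busiest times also narrows differences between nights. All of this is fair and limits what can be said about size, but none of it removes a true order effect.

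The previously-approached rule is worded inconsistently: the exclusion list names not having been approached as a ground for exclusion. The inclusion criterion and the screening description under Human Subjects Protection support the reading used here.

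Finally, baseline tobacco adjustment may already include hookah frequency. The survey items are not in the documents, so this cannot be confirmed.

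**Conclusion.** The concern holds and should be fixed. The comparison of warning with no warning is not randomised under the order described. A common first-to-second-visit change is inseparable from the warning effect on the planning basis, and with added control nights it can be separated only by assuming a form for the trend. No section acknowledges this.

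The plan's detectable differences are arithmetically right, apart from 0.01 ppm of rounding at r = 0.30, but they assume no period effect. The actual bias cannot be sized from the documents. A 1 ppm shift matters little, while shifts of about 2 to 5 ppm, well below the detectable differences, would materially distort the error rate or the power. Those rates rest on the plan's SD, correlations and 20 cafés, an assumed two-sided 5% test, and assumed shifts.

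**What to change.** Keep control-first for its stated reason, and make these changes.

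1. In the introductory section, the Design section and the Analytical Plan, describe the arm comparison as a non-randomised, fixed-order (control-first) within-café comparison in which only the message is randomised. State that order effects cannot be separated from the warning effect.
2. State that the baseline tobacco-use adjustment includes hookah use frequency from the Time 1 survey. Report by night that frequency and the number screened out as previously approached.
3. Where the café agrees, hold both nights on the same weekday and at the same hours. No short interval between them is needed.
4. Use calendar-time adjustment only as a sensitivity analysis, since it informs the order effect only in part.

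The cost is wording in three places, one named covariate and two descriptive summaries. The Time 1 survey covers hookah use and screening responses are recorded, so little or no new data collection should be needed, and no extra participants. Item 3 reduces scheduling flexibility. Order stays confounded, but openly so.

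As an option for the sponsor, randomising order with a period term would restore the randomised claim at an unchanged arm SE. It would exchange order confounding for carryover. With a 10/10 split, if earlier signs lower smoking on later control nights by c ppm, the estimated reduction shrinks by c/2, and the period term does not remove this.

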Data collection will occur outside hookah cafés in the Atlanta, GA metro area. Atlanta was chosen as the study site because Georgia's weak smoke-free air law allows smoking in bars and restaurants, including hookah cafés. There are over 100 hookah cafés in the Atlanta metropolitan area and Atlanta is home to 57 colleges and universities. The number of cafés and young adults, and the weak smoke-free air laws make Atlanta the ideal location for this study. We will partner with one pilot café and up to 31 additional cafés to allow study activities, including collecting data with customers before café entry and after café exit, and display of study-produced health warnings about hookah smoking during the times when data collection is occurring. Participants will complete data collection outside of the café at two time points, before entry into the café and after exit from the café.

Subject Selection Criteria

Participants will be those planning to enter a hookah café where the study is being conducted. We aim to have 15 participants complete Time 1 (before café entry) and Time 2 (after café exit) data collection at each café for each arm. In order to account for attrition between time points, we will enroll up to 30 participants at each café during each data collection period. We will schedule data collection periods for when the café is most busy, based on information provided by the café manager or owner.

Inclusion Criteria

- Planning to enter the hookah café where study is being conducted
- Age 18 or older
- English speakers
- Planning to smoke hookah inside
- Planning not to smoke cigarettes, cigars, cigarillos, or marijuana while at the hookah café
- Had not previously entered the café earlier in the day on the same day/night as data collection
- Has not been approached to participate in the study at another café or another day/night at the current café
- Are not employees of the business
- Have capacity to participate as determined by the staff member conducting eligibility screening

Exclusion Criteria

- Not planning to enter the hookah café where the study is being conducted
- Age 17 or under
- Non-English speakers
- Not planning to smoke hookah in the café
- Planning to smoke cigarettes, cigars, or marijuana while at the hookah café
- Are employees of the business
- Has not been approached to participate in the study previously
- Had previously entered the café on the same day/night as data collection

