The participant incentives are not intended to be an enticement to smoke hookah within the café, but rather as compensation for time needed to complete the surveys and eCO monitoring, which we anticipate will take up to 20 minutes at each time point. Participants will only be eligible if they indicate they are planning to smoke hookah in the café. We will not recruit people to come to the café, but rather recruit café customers to participants in the study. Participants will be instructed to behave as they normally would in the café. The incentive will not be able to be used in the café.

Figure 1. Table Sign

Pilot/Soft Launch

We will conduct a pilot/soft launch with a single hookah café to assess feasibility of the protocol and to make changes, if required, before conducting the full trial. Any changes to protocol and/or measures will be submitted as amendments before conducting the remainder of the trial. If no changes are made as a result of the soft launch, this café will be included in the final study sample. If significant changes are made as a result of the soft launch, we will conduct the study with up to 25 additional cafés and the data from the soft launch café will not be included in the final dataset. We will implement both text-only and pictorial warnings on different nights at the pilot café to fully test the two versions of the intervention signs, in addition to the control arm.

Outcome Measure(s)

Primary Outcome

Change in Expired Carbon Monoxide from baseline to follow-up. We will use eCO, an objective, biological marker of waterpipe tobacco consumption. There is a linear relationship between waterpipe tobacco smoking intensity and carboxyhemoglobin concentration, and eCO is strongly correlated with several topography measures of waterpipe smoking. Carbon monoxide has a half-life of 3-4 hours and is influenced by other forms of combustible tobacco; therefore, the primary outcome will be the change in eCO from before entry to after café exit, known as eCO boost. We will also record the percentage of carboxyhemoglobin concentration measured by the CO monitor.

Secondary Outcome(s)

None

Other Outcomes

Behavioral intentions. Participants will be asked at Time 2 three items assessing their expected hookah smoking within the next month. Items will be averaged to create a composite score of intent to continue the behavior within the next month.

1. How interested are you in smoking tobacco in a hookah in the next month?

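### The primary eCO-boost model uses only people who return for the exit reading, a decision made after possible exposure to the warning, and the plan has no check on who is lost in each arm

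*Combined protocol and SAP*

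**What the plan says.** The target, under Subject Selection Criteria, is 15 people per café per arm with both Time 1 and Time 2 completed. Attrition is addressed in the next sentence: "In order to account for attrition between time points, we will enroll up to 30 participants at each café". That limit applies to each collection period. Sample Size repeats the aim ("The goal is 15 completions per night, per café") and sets an overall limit: "We will enroll up to 1,560 participants in total, across the 32 cafés".

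The primary outcome is "Change in Expired Carbon Monoxide from baseline to follow-up", so it needs a reading at both times. Under Data Collection, the Time 1 survey and eCO sample are taken before entry, and Time 2 is taken after exit. Under Design, the signs are inside the café.

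The Analytical Plan bases power on completed data (20 cafés, 15 people per arm). It fits a hierarchical linear model in PROC MIXED with a fixed arm effect and random café and café-arm effects, adjusted for baseline sociodemographics and tobacco use. It defines no analysis population, missing-data assumption, report of retention by arm, or sensitivity analysis for missing Time 2 eCO. The one sensitivity analysis named compares random with fixed café effects.

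**The concern.** Enrolling more people than needed protects the number of completers. It does not protect the comparability of completers between arms. A person without Time 2 eCO has no change score, and PROC MIXED omits that record. The resulting estimate is sound if loss is ignorable given the covariates in the model, but the plan does not state that assumption. Covariates measured before entry cannot correct for loss that depends on what happened inside the café.

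Three features of the plan make such loss plausible:

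- Where a collection period ends before the café closes, participants are told to come out before it ends. Completion can then depend on length of stay, which the plan itself lists among its other outcomes.
- Data Collection lists the Time 2 survey and the payment email before the eCO sample, so a person could answer the survey and give no sample.
- Every café starts in the control arm, so any drift in retention between visits lines up with arm.

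The direction is open. Losing intervention patrons who left early or smoked little would hide a warning effect. Losing long-staying heavy smokers from that arm would exaggerate one. Fifteen completers in each arm would look balanced in both cases.

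**Working it through.** **Inputs from the documents.** Completers per café per arm, m = 15; enrolment ceiling 30 per period; overall cap 1,560 over 32 cafés; k = 20 cafés for power; SD of eCO change s = 30 ppm; r = 0.10 or 0.30 with h = r/2; 80% power; stated detectable differences 8.81 and 11.78 ppm. Alpha is not stated; two-sided 0.05 is assumed.

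**1. Reproduce the plan's benchmark.**
Detectable difference = (1.960 + 0.842) × √[(2s²/(km)) × (1 + (m − 1)r − mh)], with 2s²/(km) = 1,800/300 = 6.

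- r = 0.10: 2.802 × √[6 × (1 + 1.40 − 0.75)] = 2.802 × √9.9 = 8.815 ppm (stated 8.81).
- r = 0.30: 2.802 × √[6 × (1 + 4.20 − 2.25)] = 2.802 × √17.7 = 11.787 ppm (stated 11.78).

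One-sided 0.05 would give 7.82 and 10.46 ppm, which do not match. The benchmark is sound.

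**2. Loss the plan tolerates.**

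- At the nightly ceiling: 1 − 15/30 = 50%. With 20 cafés this needs 20 × 2 × 30 = 1,200 enrolled, within the cap.
- With the cap spread over all 32 cafés and two nights: 1,560/64 = 24.4 per night, and 1 − 15/24.4 = 38%.

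**3. Precision is not the issue.** If all 30 enrolled per period had data, the detectable difference would be 7.52 ppm (r = 0.10) or 11.07 ppm (r = 0.30). The question is bias.

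**4. Shift from completers to all enrolled.** In each arm let π be the fraction lost and D the mean boost of non-completers minus that of completers. The mean over all enrolled is the completer mean plus πD. With the effect taken as intervention minus control:

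shift = π_I × D_I − π_C × D_C

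The documents give neither π nor D, so the values below are assumptions. With the same loss in both arms, the shift is π × (D_I − D_C):

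| Loss in both arms | Shift if D differs by 10 ppm | Shift if D differs by 20 ppm | Difference in D equal to 8.81 ppm | Difference in D equal to 11.78 ppm |
|---|---|---|---|---|
| 50% | 5.0 | 10.0 | 17.6 (0.59 SD) | 23.6 (0.79 SD) |
| 38.5% | 3.85 | 7.7 | 22.9 | 30.6 |
| 20% | 2.0 | 4.0 | 44.05 | 58.9 |

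A 5 ppm shift is 57% of 8.81 and 42% of 11.78.

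With the same D in both arms but unequal loss, the shift is smaller. For D = −10, losses of 50% (intervention) and 40% (control) give −5 + 4 = −1 ppm; 40% and 20% give −4 + 2 = −2 ppm. With equal loss and equal D it is zero.

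**5. Sign.** A warning that works gives a negative effect. At 50% loss, D_I = −10 with D_C = 0 gives −5 ppm, so completers understate the benefit. D_I = +10 with D_C = 0 gives +5 ppm, so they overstate it.

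**The case against.** The plan does more about attrition than enrol extra people. The Time 2 payment is $50 against $25 at Time 1. Wristbands carry the participant ID, data collectors are stationed outside the café, and participants are told to come out in time. The model adjusts for baseline characteristics. The Time 2 survey has a branch for people who did not smoke, so a patron who was put off smoking but returns is kept. A reader might infer that over-enrolment is the whole handling of attrition; the documents do not support that.

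A reader might also infer that the plan expects to lose half its participants, or that each lost person is replaced by someone less affected. Neither is written. Thirty is a ceiling, no attrition rate is stated, and there is no replacement rule. Nor is it assured that everyone enrolled has Time 1 data: under Subject Recruitment Methods, enrolment follows eligibility and consent, and the survey and eCO sample come later.

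It is fair to add that a completers-only analysis is inferred from silence, and that imputation mainly from pre-entry data, under a missing-at-random assumption, cannot recover a reaction to the warning.

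All of this stands and limits the claim. It does not remove the gap. A change score without a missing-data method yields a completers-only estimate, retention measures may reduce loss but do not show that it is equal by arm, and nothing planned would reveal a difference.

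**Conclusion.** The concern holds as a gap in the analysis plan. As written, the primary estimate rests on people selected after possible exposure, with no stated assumption and no check on it. Under an assumed 50% loss in both arms, a 10 ppm between-arm difference in D moves the effect by 5 ppm, and 17.6 ppm moves it by the full 8.81 ppm detectable difference. At 20% loss the latter figure is about 44 ppm, so the importance of the point depends on the loss that occurs.

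A reader might conclude that the estimate is biased, or biased in a known direction. The documents do not support either: they give no loss rate by arm and nothing on how non-completers differ, and the shift is zero if loss and D are the same in both arms. The size calculation takes no credit for baseline adjustment, which would reduce the shift as far as baseline characteristics explain D. The change is advisable and the case for it is of medium confidence.

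**What to change.** Keep the hierarchical model as the primary analysis and make these additions before outcome data are seen by arm:

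1. State the analysis population and the missing-data assumption, and add Time 1 eCO to the baseline covariates.
2. Report the number enrolled and Time 2 eCO completion by arm and café, and compare completion between arms with a logistic mixed model.
3. Pre-specify a sensitivity analysis in all enrolled participants with Time 1 data. Multiply impute missing Time 2 eCO by arm, with café effects, from Time 1 eCO, Time 1 survey items, entry time and any Time 2 survey answers given without an eCO sample. Follow this with an arm-specific delta (tipping-point) analysis. The delta step is the part that addresses loss driven by reaction to the warning.

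The cost is SAP wording and modest extra analysis of data the study already plans to collect, with no extra participants or visits. The downside is that the conclusion may have to be stated as less robust if loss is high or differs by arm.
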